There is a high likelihood that the study may impact the target population of female footballers and to athletes as a wider population. The supplement of KSM-66 is easily accessible, cost-effective and has Informed Sport certification, making it safe to ingest without the risk of contaminated ingredients. The supplement is already highly used in the area of sports performance; importantly, this study aims to verify whether short-term supplementation has benefits and will inform the wider population on safe dosage guidelines. This benefits not only athletes, but practitioners on best procedure for their patients or clients. Weekly gym sessions are an integral part of footballer's training regime, and if benefits are found in muscle strength, RPE and wellness scores of sleep quality, muscle soreness, stress and fatigue, athletes may wish to explore supplementation with KSM-66 to improve their strength output, perception of difficulty, sleep quality and muscle soreness with a safe method. Additionally, if athletes or active individuals experience high levels of stress and it affects their performance and recovery as a result, the study is applicable as the intervention may potentially improve these areas.

Limitations

Regarding participants, accuracy of food reporting and following supplementation guidelines will be based on trust between the author and participant. The study has convenience sampling, which allows for ease of data collection but lacks generalisability in the sample. The focus of the study is on subjective results, without the validity of physiological tests that could measure metabolic markers, such as cortisol, from blood samples. There is also a lack of

previous research on ASH and exercise in females and athletes, which impacts result credibility.

Dissemination plan

Full transparency of the measurements will be published within each of the corresponding three papers. No measurements or scores will be omitted. The purpose of the outreach is to contribute to the scientific knowledge of ASH and its effects on muscle strength and recovery in female athletes. Additionally, this research will provide scientific knowledge to sports science and the industry of sports nutrition of the influence of short-term ASH, and whether it provides any benefits to female athletes. The methods of sharing the scientific knowledge will include presentations at conferences, exhibitions, social media and published articles in journals.

References

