Certified (specifically KSM-66, a third-party tested, branded product of ASH that is extracted from the root and without the use of alcohol or chemical solvents). If one commercial tablet of ASH supplemented daily for four weeks shows physiological benefits, it is in the athlete's best interest to cycle ASH intermittently instead of ingesting it continuously for a long duration. If four weeks of ASH supplementation does not exhibit effects, the conversation should begin on whether it is a beneficial supplement to use in general.

The justification to monitor professional female footballers' habitual food intake is to assess whether they receive adequate nutritional intake to complement their match and training schedule. It is opportunistic research, as food diaries will already be logged during the familiarisation of the muscle strength and recovery study. However, it is beneficial to analyse current dietary habits and compare it against recently published recommendations for female footballers (Dobrowolski et al., 2020). The benefit of this analysis is to potentially provide sports nutrition practitioners with insight on areas that may require improvement or attention in regard to female footballer's dietary intake and how they can be further supported.

References

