The sample size was generated using G*Power (Version 3.1.9.6). Using the peak power variable in a study analysing ASH and muscle soreness (Diehl, 2021), the estimate of the effect size of Cohen's d equals to 0.53 and therefore used in the sample size calculation for this proposed research. There is no further calculation to convert Cohen's d into Cohen's f to make it appropriate for ANOVA, as when there are only two groups Cohen's f is the same as Cohen's d (University of Michigan, 2021). Using ANOVA repeated measures between factors, effect size of 0.53, 80% power, 5% risk error in a two-parallel-group design and three measurements, the overall sample size is 30 participants, with 15 subjects per group. The calculation provided by G*Power can be found in the appendix.

Selection criteria

Inclusion for participants who are:

- Female
- Playing football professionally
- At a sub-elite to elite standard

- Healthy and free of disease

Exclusion for participants with:

- Active supplementation with other ergogenic aids
- Medication or contraceptives (to not interfere with existing treatment)
- Thyroid conditions (due to interaction with cortisol)
- Diabetes or certain autoimmune conditions (to not interfere with existing treatment)
- Active pregnancy (to not interfere with existing treatment)
- Allergies to nightshades such as tomato, aubergine, potatoes and peppers (as ASH is an herb in the nightshade group)
- No signing of the consent form

The withdrawal criteria will be participants who request to withdraw and do not wish to proceed, or do not complete the required study tests.

Intervention

The intervention will be 600mg of KSM-66, a branded supplement derived from the root extract of the herb ashwagandha, with a consistent rate of 5% withanolides for 28 days. It is the most clinically studied extract of the herb and is the only type of ashwagandha to receive third party testing certification (Informed Sport, Informed Ingredient, BSCG, Clean Label Project). The laboratory where the product is made, Ixoreal Biomed, has received Current Good Laboratory Practices (cGLP), quality controlled and tested against heavy metals and pesticides.

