Food diary analysis research, compared against (Dobrowolski et al., 2020):

- Energy intake (kcal)
- Energy availability (kcal/kg fat free mass/day)
- Protein (g/day)
- Carbohydrates (g/day)
- Fat (%)
- Fluids (L/day)
- Vitamin D (mg/day)
- Calcium (mg/day)
- Iron (mg/day)

All data will be collected via Snap-N-Send and stored using Nutritics dietary analysis software (Research Edition, v5.096, Dublin, Nutritics, 2019). The Snap-N-Send method was analysed in a doubly labelled water study and was shown to have enhanced validity for assessing athlete total energy intake (Costello et al., 2019). The Nutritics software was clinically studied to be a useful and valid tool for healthcare professionals to measure macronutrients and micronutrients, demonstrating that its analysis values positively correlated with plasma markers (Watkins et al., 2020)

Independent:

- The treatment of ASH: 600mg KSM66 (30mg withanolides) once a day for 28 days

Data collection

Study data will be collected manually and entered into Blanquerna's OneDrive system. All data sheets and files will be backed up on to Google Sheets and shared with associated researchers and tutors of the project. This allows for data to be reviewed by collaborators.

Dietary intake data will be collected via Whatsapp using Snap-N-Send. The data will then be manually entered and stored using Nutritics and access will be shared with collaborators.

Data analysis

For the muscle strength and recovery research, dependent variables will be described as the mean and standard deviation and calculated using and **ANOVA repeated measures, between factors** as there will be three time points. A descriptive analysis will be carried out for all the data collected in the data collection notebook. To assess the normality of the data distribution, the **Kolmogorov-Smirnov** test will be used.

For the food diary analysis, dependent variables will be described as the mean and standard deviation and determined using **one-sided t-test** to compare against data averages of nutritional recommendations for female footballers (Dobrowolski et al., 2020). **Pearson's r** will be used to examine correlations between the selected variables.

Ethical considerations

The ethical considerations for this study are predominantly the safety, comfort and consent of the participant:

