There is no known conflict of interest in this study. There will be no plagiarism within this study and all words will be original to the study. There will be no fabrication or invention of results, and data will be analysed and published accurately and transparently. All collaborators will be employed staff members of the football club who are collaborating in the thesis. The gym facilities where the tests will be measured and performed are on-site of the football club and where the players have weekly gym training sessions. The gym facility is a licensed establishment. The participants will be informed of the results and will have access to their individual data.

Work plan

A visual representation of the study timeline can be found in the appendix. A description of each step is as follows:

0. Approval from the ethical committee
1. Participants are informed about the aims of the study and sign the consent form. Information about age, BMI, years of practice and health history is collected
2. Participants start tracking their food diaries via an app remotely for three days over the weekend prior to the supplementation for familiarisation
3. Baseline measures for muscle strength will be taken on the following day at the club gym, coinciding with a regular gym training session. The measures will be taken prior to starting a typical training session
4. The team will consist of the author ([name]), [name] and [name] who will assist with data collection and physiotherapist [name] who will monitor participants and their safety while performing the strength tests

5. Afterwards participants will be given a printout of the TQR questionnaire and the Hooper Index to complete for the next day. Participants will be given their course of supplementation, either placebo or KSM-66, and instructed to take one a day for 28 days
6. The following day, baseline measures for the muscle recovery will be collected remotely at midday via Whatsapp or Zoom, and at the same time participants will start supplementation of either KSM-66 or placebo
7. Fourteen days later, participants perform the muscle strength tests in the evening at the club gym. Similar to before, the team will consist of the author ([name]), [name], who will assist with data collection and physiotherapist [name] who will monitor participants' safety while performing the strength tests

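### Cohen's d = 0.53 was entered in G*Power as Cohen's f; for two equal groups f is half of d, so 30 participants give about 30% power on the plan's own model, not 80%

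*Combined protocol and SAP*

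**What the plan says.** Under Methodology, Sample size, the plan reports from an earlier ashwagandha study that "the estimate of the effect size of Cohen's d equals to 0.53" for peak power. It makes no conversion to Cohen's f because "when there are only two groups Cohen's f is the same as Cohen's d". The G*Power entry is then given as "effect size of 0.53, 80% power, 5% risk error in a two-parallel-group design and three measurements, the overall sample size is 30 participants", 15 per group. The procedure is the between-factors repeated measures ANOVA, and the Data analysis section names the same test for the strength and recovery outcomes: "ANOVA repeated measures, between factors".

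On timing, Work plan step 3 says "Baseline measures for muscle strength will be taken on the following day at the club gym". Step 6 places the first capsule a day after that, when the recovery baseline is collected: "at the same time participants will start supplementation of either KSM-66 or placebo". The first strength measurement is therefore untreated in both groups.

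On interpretation, the Justification of the study says that if four weeks of supplementation shows no effects, "the conversation should begin on whether it is a beneficial supplement to use in general".

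**The concern.** Cohen's d is the difference between two means divided by the within-group SD. Cohen's f is the SD of the group means divided by the within-group SD. With two equal groups each mean lies d/2 from the grand mean, so f = d/2. Treating the two as equal doubles the assumed effect.

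This is the only power statement in the plan. If it is wrong, a between-groups test on 30 participants would more often than not miss the effect the plan assumes, unless the correlation is well below 0.5. The remark in the Justification is not a decision rule, but a reader who trusts 80% power would give a null result more weight than it can bear.

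**Working it through.** **Inputs.** From Sample size: d = 0.53, alpha 0.05, two equal groups, m = 3 measurements, N = 30. The correlation among repeated measures (rho) is not in the readable text, because the content of the appendix's sample size calculation did not survive PDF reading. It is treated as an assumption over 0 to 1.

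**Model.** For G*Power's between-factors repeated measures ANOVA, the test is F on (1, N − 2) degrees of freedom with noncentrality

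lambda = N × f² × m / (1 + (m − 1) × rho).

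**Step 1: reproduce the plan's figure.** With f = 0.53, the total N for 80% power is 22 at rho 0.5, 28 at rho 0.8, and 30 at rho 0.90 to 1.0. At rho 1.0, lambda = 30 × 0.2809 × 3/3 = 8.43 and power at N = 30 is 80.0%. So 0.53 was used as f.

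**Step 2: correct the conversion.** f = 0.53/2 = 0.265 and f² = 0.0702. At N = 30:

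| rho | lambda | Power | d needed for 80% power | Total N for 80% at d = 0.53 |
|---|---|---|---|---|
| 0 | 6.32 | 68.0% | – | 40 |
| 0.5 | 3.16 | 40.4% | 0.87 | 78 |
| 0.8 | 2.43 | 32.5% | 0.99 | 100 |
| 0.9 | 2.26 | 30.6% | 1.02 | 108 |
| 1.0 | 2.11 | 28.9% | 1.06 | 114 |

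Check: at rho = 1 the model reduces to a two-sample t-test with 15 per group, which has 28.9% power at d = 0.53 and 80.0% at d = 1.06.

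**Step 3: allow for the untreated baseline.** The model takes the group difference to be present at all three measurements. If the differences are 0, 0.53 and 0.53, the average is 1.06/3 = 0.353 and f = 0.177. Power for the between-groups main effect is then 20.8% (rho 0.5), 17.1% (0.8) and 16.2% (0.9). Simulation with 20,000 runs gave 20.6%, 16.7% and 15.7%.

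**Step 4: what a null result would show.** The 95% CI half-width for the group difference averaged over three measurements, in SD units, is

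t(0.975, 28) × √(2/15) × √((1 + 2 × rho)/3) = 2.048 × 0.365 × √((1 + 2 × rho)/3),

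which is 0.61 (rho 0.5), 0.70 (0.8) and 0.72 (0.9). At these correlations even an observed difference of zero leaves 0.53 inside the interval.

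**Step 5: other tests, for comparison.** All are for d = 0.53 at N = 30.

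| Test | 0.5 | 0.8 | 0.9 |
|---|---|---|---|
| Group-by-time, differences 0, 0.53, 0.53, compound symmetry (by rho) | 28.9% | 63.2% | 91.5% |
| ANCOVA, one follow-up value adjusted for baseline (by baseline correlation r) | 36.6% | 64.5% | 89.4% |

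The ANCOVA row uses noncentrality d × √(15/2)/√(1 − r²) on 27 degrees of freedom. Simulation with 20,000 runs gave 35.4%, 63.2% and 88.5%.

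**The case against.** The best defence is that the trial may be less weak than 30% suggests. A repeated measures ANOVA ordinarily also yields a group-by-time term. At rho 0.9, one of the values that reproduces N = 30, that term has 91.5% power for the same effect, and ANCOVA is close behind. This stands as a statement about other tests. It does not rescue the stated 80%, which was computed for the between-groups test, the one named in both Sample size and Data analysis. Nor is it robust, since group-by-time power falls to 28.9% at rho 0.5.

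Four smaller points also have some force:

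- The 40% figure belongs to rho 0.5, at which the plan's inputs would have given 22 participants, not 30. The figure closest to the plan's own calculation is 29% to 31%; 40% is sensitivity.
- The statement that a zero difference would not exclude 0.53 applies to the three-measurement average and fails at low correlation (half-width 0.51 at rho 0.2). For ANCOVA at r = 0.9 the half-width is about 0.33, and zero would exclude 0.53.
- The correlation may be in the appendix output, so its absence from the readable text is not counted against the plan. Whether the source d was a between-group or a within-group effect cannot be checked either; the plan uses it as between-group.
- Scientific-technical validity describes two measurements, while Sample size and the Work plan describe three. With two, corrected power is 37% (rho 0.5) or 30% (rho 0.9), so this does not restore 80%.

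**Conclusion.** The concern holds. The equality of f and d is an error of definition, and the stated 80% power is wrong for the named test at every correlation from 0 to 1. At correlations that reproduce the plan's 30 participants, power for d = 0.53 is 29% to 31%; it is 33% at 0.8 and 40% at 0.5. With the pre-supplement baseline allowed for, it is about 16% to 21% (rho 0.9 to 0.5). These figures assume that 0.53 is a between-group standardised difference, that the groups are equal, and that the correlation is common to all pairs of measurements. They concern the between-groups main effect only; the chance of detecting an effect with another test depends strongly on the test and on the correlation. This must be corrected before the plan is relied on.

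**What to change.** Keep 30 participants and correct the Sample size paragraph:

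1. Delete the statement that f equals d and write f = d/2 = 0.265.
2. State the assumed correlation among repeated measures in the text, repeating it from the appendix if it is already there.
3. Restate the power for d = 0.53 at 30 participants as about 30% on the between-groups model (29% to 31% at rho 0.90 to 1.0, 33% at 0.8, 40% at 0.5), and note that it is about 16% to 21% once the untreated baseline is allowed for. Alternatively, give the detectable effect at 80% power on that model: d of about 0.87 at rho 0.5, 0.99 at 0.8, and 1.02 to 1.06 at 0.90 to 1.0.
4. If a baseline-adjusted comparison of one follow-up value (ANCOVA) is adopted as the main test instead, name it in Data analysis and quote its power with the baseline correlation: 36.6% at 0.5, 64.5% at 0.8, 89.4% at 0.9.
5. State that a non-significant result is inconclusive for d = 0.53 unless the 95% confidence interval excludes it.

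The cost is one reworded paragraph and a G*Power re-run, plus an edit to Data analysis if ANCOVA is chosen. The drawback is a less favourable power figure. Restoring 80% on the present model by enrolment would take 78 to 114 participants (rho 0.5 to 1.0), and recruitment is from a single club; that is why the fix restates the power and does not ask for a larger sample.

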A highly important factor of KSM-66 is its sole use of extraction from the root of ashwagandha, thereby avoiding the leaves. Extracts derived from the leaf contain Withaferin A and Withanone, which are considered cytotoxic (Priyandoko et al., 2011; Khedgikar et al., 2015; Rossato Viana et al., 2022). A paper by (Siddiqui et al., 2021) states that Withanone is the active metabolite that can induce liver toxicity with overuse. In a previous case report by (Björnsson et al., 2020), liver injury of moderate severity was reported in five patients after

supplementing ashwagandha. The listed ashwagandha supplements responsible for the injuries had no information on extraction process or what part of the herb was used, no certification and had unstated levels of withanolides.

This amplifies the importance of sole root extraction, controlled levels of withanolides and third-party testing for ashwagandha supplements, such as KSM-66. The safety and tolerability of root-extracted KSM-66 is evident in scientific literature (Raut et al., 2012; Sharma et al., 2018; Salve et al., 2019). In a trial by (Verma et al., 2021b) body weight, body temperature, pulse rate, respiratory rate, systolic and diastolic blood pressure, haematological and biochemical parameters were analysed to be normal in males and females after 8 weeks of daily consumption of 600mg KSM-66.

Muscle strength will be predominantly based on the data from the hand grip test using the hand-held dynamometer, CAMRY model. The participants will squeeze the dynamometer with all their ability on each hand, and the strength values will be determined by an average of each hand's measurement.

During the 28 days, participants will have 12 training sessions and 4 official matches. It is likely the participants will experience menstruation during the study. However, recent findings suggest there is no change in strength or exercise performance from short-term fluctuations in reproductive hormones (Colenso-Semple et al., 2023).

Dosage

For 28 days, participants in the experimental group will ingest 600mg KSM-66 (30mg withanolides) once daily at midday with a meal. Participants in the control group will ingest a HPMC capsule containing 600mg of chickpea flour once daily at midday with a meal.

Potential benefits

Benefits will vary between subjects, however ASH supplementation may:

- Reduce levels of cortisol, resulting in:
 - Improved sleep
 - Improved muscle strength

- Improved cardiorespiratory fitness

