- Improved perception of recovery
- Reduced difficulty of exertion during exercise

(Bonilla et al., 2021)

Potential side effects

Side effects of ASH are uncommon, however large doses (exceeding 1,250mg daily, based on a clinical trial examining tolerability) may induce:

- Direct irritation to the intestinal mucosa, resulting in:
 - Nausea
 - Vomiting
 - Gastrointestinal upset

(Raut et al., 2012, LiverTox, 2019)

Regarding the potential side effects of KSM-66 specifically, a trial by (Chandrasekhar et al., 2012) noted adverse effects in subjects after 60 days of 600mg KSM-66 supplementation. Overall, there were 6 adverse events with ASH and 5 with placebo. They included congestion, decreased appetite, cough and cold symptoms. The placebo group experienced fever, headache, tiredness and abdominal pain, making it unclear as to whether KSM-66 has notable or established side effects.

Intervention group

The intervention for the experimental group will be KSM-66 ashwagandha (600mg ashwagandha containing 30mg withanolides, once a day with meals for 28 days, ingested at midday) supplied by the company Zenement based in Barcelona. The branded product of KSM-66 is made by Ixoreal Biomed.

Control group

The control group will receive rice flour in a HPMC capsule, once a day with meals for 28 days, ingested at midday. The rice flour will be a commercial product found in supermarkets. To achieve randomisation, simple random allocation will be used to prevent bias amongst participants. The protocol will follow the randomisation guide by (Arifin, 2012) and will be

achieved in SPSS software. It will be a double-blind study as the main researcher will not know which participants supplement ASH or placebo.

Variables

Dependent:

Muscle strength research:

- Hand grip strength in kilograms (kg) using a CAMRY dynamometer. The variable of interest will be the mean of the right and the left-hand measurements
- Seated medicine ball throw in metres (m)
- Counter movement jump (CMJ) in watts per kilogram ($W \cdot kg^{-1}$)
- Squat jump (SJ) in centimetres (cm),
- Peak power in watts per kilogram ($W \cdot kg^{-1}$), using the results from SJ
- Rate of Perceived Exertion (RPE) via Borg Scale

Muscle recovery research:

- Perceived ratings of sleep, stress, fatigue and Delayed Onset Muscle Soreness (DOMS) via Hooper Index (HI)
- Total Quality Recovery (TQR) questionnaire
- Supplement satisfaction questionnaire

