There is minimal risk posed to participants involved in this study, as there are no reported harms from supplementing KSM-66 in clinical research and no adverse effects have been reported. Additionally, it is a commercially available product that has been certified safe to supplement. As KSM-66 is made from root extraction of the ashwagandha herb, and therefore not made of the leaves, there is less toxicological risk as the metabolites Withaferin A and Withanone are removed in the process (further elaboration in the *Thesis – Intervention* section of this document) making KSM-66 safer than other products of ashwagandha. Potentially, a participant could have an undiagnosed illness or allergy to nightshades and the supplement gives side-effects. Previous literature has not reported any instances of this happening. It is unlikely as athletes typically have a medical team at their disposal, who provide health checks and make sure they are fit to play. Due to the short-term time length and reasonable dosage of the study, there is minimal risk for over-supplementation leading to consistently reduced cortisol or gastrointestinal problems. There is low to no risk pertaining to psychological, social or economic factors. The study has been designed with participant comfort in mind and the timeline, training sessions, performance and recovery tests mimic the participants' usual regime, allowing for ease of participation and reduced risk factor.

The anticipated benefits outweigh the risks. The supplement of KSM-66 has shown to improve muscle strength, recovery, cognition and sleep in published literature. These are highly important factors to the lifestyle of an athlete and provide social, psychological and physical benefits.

Privacy

All personal data and information collected or generated in the study will be stored on OneDrive Blanquerna and protected in accordance with the current legislation on personal data protection (Regulation (EU) 2016/679 and in the Organic Law 3/2018 of 5 December on Data Protection). No one, except some of the staff directly related to this study, will be able to know the identity. Data will be stored only for the duration of the study and during the process of analysing the data.

Integrity

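### The allergy exclusion covers only the active capsule, so a player with a known allergy to the placebo flour meets the listed criteria and has an even chance of receiving it

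*Combined protocol and SAP*

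**What the plan says.** The exclusion list under Methodology, Selection criteria, names one group of allergies: "Allergies to nightshades such as tomato, aubergine, potatoes and peppers (as ASH is an herb in the nightshade group". The reason given is the botanical family of the active herb. No criterion names legumes, cereals, the capsule shell or food allergy in general. The nearest general criterion is the inclusion "Healthy and free of disease".

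The control capsule is described twice. Under Dosage: "Participants in the control group will ingest a HPMC capsule containing 600mg of chickpea flour once daily at midday with a meal". Under Control group: "The control group will receive rice flour in a HPMC capsule, once a day with meals for 28 days, ingested at midday".

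The Benefit / risk ratio section raises allergy once: "Potentially, a participant could have an undiagnosed illness or allergy to nightshades and the supplement gives side-effects". It does not discuss the control capsule as an exposure.

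On allocation, the Control group section says "simple random allocation will be used to prevent bias amongst participants", and the Sample size section says "the overall sample size is 30 participants, with 15 subjects per group". The trial is described as double-blind. Work plan step 1 collects health history at consent, with no stated eligibility rule attached to filler allergy.

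**The concern.** In a randomised trial, eligibility has to be judged against every treatment a participant might be allocated. Here the allergy criterion was written for one of the two capsules. The other contains a food flour, which is itself a possible allergen, and it is taken once a day for up to 28 days.

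What is at stake is avoidable harm to a player whose allergy was already known and could have been asked about. Under blinding, neither she nor the main researcher would know which capsule she was taking, so a reaction could not readily be traced to the filler at the time. The two descriptions of the placebo make this harder. Until they agree, nobody can say which allergen the screening question should name.

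**Working it through.** No figure in the plan has to be recalculated except the chance of receiving placebo. The rest is a comparison of sections.

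**1. Chance of the control capsule.** From the Sample size section, N = 30 with 15 per group. With a fixed split the chance for any one player is 15/30 = 0.50. With simple allocation to two equally likely arms it is also 0.50. *An even chance* is therefore right under either reading of the allocation method.

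**2. Criteria against capsule contents.**

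| Component | Where described | Covered by a written allergy criterion? | Covered in the risk text? |
|---|---|---|---|
| Ashwagandha root extract | Intervention, Dosage | Yes (nightshades) | Yes |
| Chickpea flour, 600 mg | Dosage | No | No |
| Rice flour, mass not given | Control group | No | No |
| HPMC shell | Dosage and Control group (control capsule) | No | No |

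Whichever flour is used, the answer in its row is the same. The gap does not depend on how the contradiction is settled, but the wording of the remedy does.

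**3. Does the general health criterion close it?** The plan did not rely on that criterion for nightshade allergy, thyroid conditions or diabetes. Each is listed separately. It would be inconsistent to read it as covering a different food allergy.

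**4. How likely is an affected player?** The documents give no prevalence of allergy to either flour. For illustration only, assume a prevalence p between 0.1% and 3% and treat players as independent. The probability of at least one affected player among n is 1 − (1 − p)^n.

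| Assumed p | Among 30 enrolled | Among 15 controls |
|---|---|---|
| 0.1% | 1 − 0.999^30 = 3.0% | 1 − 0.999^15 = 1.5% |
| 1% | 1 − 0.99^30 = 26% | 1 − 0.99^15 = 14% |
| 3% | 1 − 0.97^30 = 60% | 1 − 0.97^15 = 37% |

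The control-arm column runs from 1.5% to 37%, a factor of about 25 that comes entirely from the assumption. It counts allergic players, not reactions. Harm also requires that the player enrols, that no health check picks up the allergy, and that the amount in the capsule provokes a reaction. The figures are therefore upper limits at each assumed p, and none of them should serve as a headline.

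**The case against.** The strongest case on the other side is that the trial has several informal safeguards. Health history is taken at consent. The recruiting liaison at the club already knows the players' health background. The Benefit / risk ratio section refers to medical-team checks. Three days of food diaries precede supplementation, and two registered sports nutritionists are involved. There is a check-in after a week, and a player may leave at any time. Any of these could bring a known food allergy to light or cut short an exposure. This stands as a reason to think the risk small. It does not close the gap, because no written rule says what happens once such an allergy is found.

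A reader might infer more than the documents support:

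- *That players are not told what the placebo contains.* This cannot be asserted. The consent pages are not available for review, and the recruitment presentation is described as giving full study information.
- *That an affected player would take 28 daily doses of 600 mg.* That is a worst case. The 600 mg mass is stated only for chickpea, and a player who reacted could stop.
- *That reactions among controls would bias the result toward ashwagandha.* Such a reaction could in principle depress that arm's recovery and satisfaction scores or cause a dropout, and one player is 1/15 = 6.7% of the arm. But this supposes a reaction that may never occur, and no mechanism is apparent for hand grip, the main strength measure. It is speculation, not a finding.

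**Conclusion.** The point holds as an eligibility and safety gap, and no further. The only allergy exclusion and the only allergy risk discussed concern the active capsule. A player with a known allergy to the control filler is eligible on the listed criteria and has a 50% chance of receiving it. The conclusion rests on the visible Selection criteria, on the even split, and on the control capsule holding a food flour, which both descriptions agree on even though they name different flours.

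The probability that such a player enrols is unknown and probably low, since it depends on a prevalence the documents do not give. The point leaves the primary analysis untouched and does not show that the trial's comparison would be biased. It is a minor point, worth making because the harm is avoidable and the correction is nearly free.

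**What to change.** 1. Reconcile the Dosage and Control group sections so that the placebo has one stated composition, including the filler and its mass. Which flour is used is for the sponsor to settle.
2. Extend the existing allergy exclusion so that it covers known allergy to any declared component of either study capsule, not only nightshades. Make the matching change to the allergy sentence in the Benefit / risk ratio section.
3. Add one question on this to the health history in Work plan step 1, asked of every player before allocation, so that the answer feeds the eligibility decision.

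The cost is a few lines of protocol text and one screening item. Few if any eligible players should be lost. Because the question covers both capsules and is asked before allocation, it does not affect blinding, the schedule or the analysis.
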